6.2.1 Immune Monitoring Studies

At each time point in the previous table nine 10 cc green top tubes and one 10 cc red top tube will be collected. An additional serum sample (one 10 cc red top tube) will be collected at week 14.

All blood samples will be sent to Translational Therapy Laboratory (TTL) at University of Minnesota. Refer to the affiliate lab manual for the specimen specific shipping instructions.

T, NK, Treg by immunophenotype, NK cell function [CD107a and IFN production] measurements will be done in peripheral blood and tumor tissue at the Translational Therapy Laboratory (TTL) at University of Minnesota.

ELISPOT to PA2024, ELISA to measure antibody to PA2024 will be done at above specified time points from the peripheral blood by Dendreon.

Serum kynurenine, tryptophan, K/T ratio, and indoximod levels will be measured from peripheral blood at the specified time points by Newlink.

The pre and week 14 serum sample will be analyzed for immune biomarkers by Newlink.

If the patient consents at time of enrollment, aliquots of leftover serum will be stored from each blood draw at -80 degrees C in the Masonic Cancer Center's TTL for future testing. Permission to store leftover samples will be embedded in the treatment consent.

6.2.2 Optional Biopsies

Patients with an intact prostate or a metastatic site that can be easily biopsied will be invited to participate in this optional component of the research at the time of consent.

Biopsy solely for research would be done prior to first leukapheresis and at 14 weeks from the first infusion of sipuleucel-T. Patients with an intact prostate that has not received prior radiation will be preferred over a metastatic site.

The core biopsy will be assessed for expression of Treg, T cells (CD4+ /CD8+), and NK markers. Part of the formalin-fixed paraffin embedded tumor tissue will be sent by the University of Minnesota to the laboratory of [name] for IDO expression by immunohistochemistry (IHC).

Refer to the affiliate lab manual for the specimen specific shipping instructions to the University of Minnesota BioNet.

7 Study Drug (Indoximod/Placebo) Information

In this section, study drug is used as a general term referring to both indoximod and the identical looking placebo.

7.1 How Supplied

Indoximod is sterile tan powder compounded in capsule form of 200 mg. The capsules are packaged 175 capsules per bottle in white opaque HDPE bottles. The placebo consists of 313 mg of Microcrystalline Cellulose, NF in the identical #0el capsule used for indoximod capsules.

7.2 Manufacture and Control

Indoximod is manufactured according to current Good Manufacturing Practice guidelines and NewLink Genetics Corporation specifications by a contracted manufacturing facility. Indoximod is tested against established quality specifications by the contractor and released for clinical use by NewLink Genetics Corporation Quality Assurance. Indoximod components intended for use in the clinic are placed on stability testing according to International Conference on Harmonization (ICH) guidelines to ensure that it meets specifications during the course of the clinical trial.

The placebo product is manufactured according to current Good Manufacturing Practice guidelines and NewLink Genetics Corporation specifications by a contracted manufacturing facility. The placebo products are tested against established quality specifications by the contractor and released for clinical use by NewLink Genetics Corporation Quality Assurance. Placebo components intended for use in the clinic are placed on concomitant stability testing according to International Conference on Harmonization (ICH) guidelines to ensure that it meets specifications during the course of the clinical trial.

7.3 Drug Procurement

Indoximod (drug product) and placebo is shipped directly to the clinical sites at the direction of NewLink Genetics Corporation. Storage and audit of all Quality Control and Quality Assurance documentation will be performed by NewLink Genetics or designee. Indoximod/placebo is shipped by a carrier to the clinical site at room temperature. Each shipment is accompanied by a Drug Shipment Receipt Form.

7.4 Drug Accountability

As required by FDA regulations, all drug storage, procurement and usage will be carefully monitored and documented. The Principal Investigator and Sponsor will oversee this process and delegate responsibility as needed. A careful inventory will be maintained at NewLink Genetics Corporation and at the clinical sites.

7.4.1 Drug Receipt and Inventory:

The PI or designated individual will:

- Complete a Drug Request Form and send to NewLink Genetics. NewLink will make the appropriate arrangements for shipment of the drug from the manufacturer.
- Upon receipt of the investigational drug, inventory the shipment ensuring that the information on the packing slip matches exactly with what has been sent to the site, including the amount, lot numbers provided inventory form.
- Promptly bring any discrepancies, breakage or evidence of tampering to the attention of NewLink Genetics.
- Retain a copy of the shipping inventory, packing slips, and documentation of inventory in the study's records.

7.4.2 Drug Storage

The study drug must be stored in a secure environment, with access limited to essential and appropriate research personnel. The drugs should be kept locked in a cabinet in a locked/secure area. The study drugs should be stored at controlled room temperature (within the range of 18° –25° C or 64° – 75° F) and a storage area daily temperature log should be maintained and available for monitoring at all times. Shelf-life surveillance of the intact bottles is on-going.

7.4.3 Drug Labeling

The study drug bottles are pre-labeled and the labels should not be defaced or changed in any way without written permission of NewLink Genetics. It is recommended that an additional label be placed to include the subject initials, subject study number, date dispensed, name of institution, study staff contact name and phone number. NewLink will provide these labels for the clinical site.

7.4.4 Drug Dispensing

Study drugs will be dispensed only by those who are authorized by the IRB approved protocol, principal investigator, state and federal regulations, and NewLink Genetics.

Study drugs will be dispensed according to the dose, route, and frequency written in the clinical protocol. The PI shall dispense or

administer the study drug only to subjects under his/her personal supervision or under the supervision of a co-investigator. The investigator shall not dispense or supply the study drug to any person not authorized to receive it.

A study medication binder will be created to include specific dispensing instructions, drug accountability form, record of drug dispensing, drug shipment form, and drug return form and labels.

Study drug will be properly accounted for and tracked with adequate documentation (study medication diary). Each time the study drug is dispensed; there should be documentation as to the amount dispensed, to whom it is dispensed, and the date and signature or initials of the person dispensing the drug.

Subjects will be instructed in the proper storage, use and precautions, and potential known risks of the study drug. Subjects should be advised to return all used and unused containers/units to the site of original dispensing. Study personnel should record the amount (number of bottles and pills, etc.) and date of return. Attempts to retrieve the containers/units from subjects who have not returned them should be documented. Any discrepancies between the amounts used by subjects (actual or suspected) and the amount returned should be documented, as well as the reasons for the discrepancies.

7.5 Breaking the Blind

The blind shall be maintained throughout the conduct of the trial unless it is felt necessary to break the blind in a specific case in the interest of patient safety. In general, the blind will be broken after all the data are recorded, locked, and analyzed. The study statistician ([name]) will provide each site's investigational pharmacy with the treatment code key. Any request to break a blind will be discussed with the sponsor/investigator ([name]) and NewLink.

7.6 Return/Destruction of Study Drug

At the conclusion of the study ensure that all documentation regarding receipt, storage, dispensing, return of used containers, and accountability is complete and accurate. Unused drug obtained from NewLink Genetics must be returned to NewLink or be destroyed on site using appropriate procedures upon written authorization from NewLink to do so.

8 Adverse Event Documentation and Reporting

Toxicity and adverse events will be classified according to NCI's Common Terminology Criteria for Adverse Events V 4.0 (CTCAE) and reported on the schedule below. A copy of the CTCAE can be downloaded from the CTEP home page

(http://ctep.cancer.gov/protocolDevelopment/electronic_applications/ctc.htm#ctc_40).

8.1 Definitions

The following definitions are based on the Code of Federal Regulations Title 21 Part 312.32 (21CFR312.32(a)).

Adverse Event: Any untoward medical occurrence associated with the use of a drug in humans, whether or not considered drug related.

Suspected Adverse Reaction: Any adverse event for which there is a reasonable possibility that the drug caused the adverse event.

Life-Threatening Adverse Event Or Life-Threatening Suspected Adverse Reaction: An adverse event or suspected adverse reaction is considered "life-threatening" if, in the view of either the investigator or sponsor, its occurrence places the patient or subject at immediate risk of death.

Serious Adverse Event Or Serious Suspected Adverse Reaction: An adverse event or suspected adverse reaction is considered "serious" if, in the view of either the investigator or sponsor, it results in any of the following outcomes:

- Death
- A life-threatening adverse event
- Inpatient hospitalization or prolongation of existing hospitalization
- A persistent or significant incapacity or substantial disruption of the ability to conduct normal life functions
- A congenital anomaly/birth defect.

Important medical events that may not result in death, be life-threatening, or require hospitalization may be considered serious when, based upon appropriate medical judgment, they may jeopardize the patient or subject and may require medical or surgical intervention to prevent one of the outcomes listed in this definition.

If either the IND sponsor or the investigator believes the event is life-threatening or serious, the event must be evaluated by the sponsor for expedited reporting (21CFR 312.32(a)).

Unexpected adverse event or unexpected suspected adverse reaction: An adverse event or suspected adverse reaction is considered “unexpected” if it is not listed in the investigator brochure or is not listed at the specificity or severity that has been observed; or, if an investigator brochure is not required or available, is not consistent with the risk information described in the general investigational plan or elsewhere in the current application, as amended. Thus, adverse events that occur as part of the disease process or underlying medical conditions are considered *unexpected*; however, they will not be reportable per 8.3.

8.2 Adverse Event Documentation

Monitoring for adverse events will begin with the signing of the consent and continue through the final treatment visit approximately 30 days after the last dose of indoximod/placebo.

For the purposes of this study, adverse event documentation requirements will be determined based on grade, expectedness and relationship to study therapy as follows:

	Grade 1	Grade 2		Grade 3		Grade 4 and 5
	Expected or Unexpected	Expected	Unexpected	Expected	Unexpected	Expected or Unexpected
Unrelated Unlikely	Not required	Not required	Not required	Not required	Required	Required
Possible Probable Definite	Not required	Not required	Required	Required*	Required*	Required*

*any grade 3 treatment related event that does not resolve to a grade 2 or better within 7 days and any grade 4 and 5 events will be considered excess and count toward an early termination event per section 12.2. Such events must be reported on the early study stopping event form found in OnCore.

In addition, although not always a reportable event, deaths (date and cause) will be recorded in OnCore upon knowledge in the follow-up tab.

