1.2 Secondary Objectives

- To assess the safety of indoximod when administered post sipuleucel-T therapy
- To assess efficacy as measured by improvement in time to disease progression, objective response rate, overall survival
- To assess health related quality of life improvement on therapy

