2.2 Sipuleucel-T (Provenge)

After decades of promise and research, sipuleucel-T (Provenge) has been the first vaccine therapy approved for treatment of any cancer in the United States. Sipuleucel-T involves *ex-vivo* sensitization of peripheral blood mononuclear cells to a custom prostatic acid phosphatase and granulocyte monocyte – colony stimulating factor (GM-CSF) fusion protein (PA 2024) followed by autologous transfusion. Sipuleucel-T is very well tolerated with mostly grade 2 side effects consistent with cytokine release. It has shown to improve survival by 3-4 months as compared to placebo in randomized, double blinded phase III clinical trials.(2, 3) Besides this modest improvement in survival, there has been no improvement in time to objective disease progression or an objective response rate (>25% decline in PSA).(2, 3) Although this has been a huge first stride in development of immunotherapies and first proof of principle, additional progress needs to be made before this technology has its fullest and most widely-applicable impact in treating cancers of prostate and other malignancies.

2.3 1-methyl-D-tryptophan (1-MT, indoximod)

Indoleamine 2,3-dioxygenase (IDO) is a key immune-modulatory enzyme that degrades tryptophan to bioactive kynurenine metabolites. The process and effects of tryptophan depletion and kynurenine metabolism together form the immuno-modulatory IDO pathway(4), which promotes peripheral immune tolerance by direct inhibition of effector T cells, activation of pre-existing Foxp3+ Tregs, and conversion of naïve T cells to Tregs. 1-MT is a competitive inhibitor of the immunoregulatory enzyme, IDO, a critical regulator of immunosuppressive responses.

In the preclinical studies, 1-MT was readily absorbed following oral administration in mice, rats, and dogs and the bio-availability ranged from 85 to 100%(6). It was determined to be safe in rats and pigs at doses as high as 3000 mg/m²/day (500 mg/kg/day) administered for 4 weeks and no significant clinical, hematology or chemistry abnormalities were noted.

In preclinical studies severity of toxoplasmosis was increased and activation of latent toxoplasmosis was noted in mice (unpublished data/7). Experimental colitis and encephalitis in preclinical studies were worsened by administration of 1-MT, although colitis and encephalitis have not been noted by administration of 1-MT alone. (8,9).

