When indoximod (1-MT) used immediately post sipuleucel-T as in this clinical trial, it might increase the side effects of cytokine release from last infusion of sipuleucel-T.

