11.2 Secondary Endpoints

- Antibodies to PA2024 as measured by ELISA
- Progression free survival
- Objective response rate as defined by Prostate Cancer Working Group -2 (PCWG2)(6)
- Overall survival and survival at two years
- Safety and tolerability
- Health related quality of life

12 Statistical Considerations

Our primary analysis will compare Tcell activation to PA2024 as measured by ELISPOT at 14 weeks between treatment groups using the two-sample t-test for unequal variance. This analysis will be completed on log-transformed data in the event that Tcell activation is skewed. A secondary analysis will be completed adjusting for any potential confounders or baseline differences using linear regression.(11)

Secondary endpoints CD54 count, antibodies to PA2024 and Tcell proliferation will be compared between groups in an unadjusted analysis using the two-sample t-test and an adjusted analysis using linear regression. Response rate will be summarized by group using contingency tables and the odds ratio for response will be estimated using logistic regression. Time to disease progression and overall survival will be summarized by Kaplan-Meier Curves and the hazard ratio estimated using Cox regression. In addition, quality of life will be measured by the FACT-P (a validated questionnaire consisting of four subscales of well-being: Physical, Social/Family, Emotional and Functional) and compared between treatment groups using the two-sample t-test for univariate analyses and multivariate linear regression for multivariate analysis.

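### The section 8.2 documentation rule does not assure a complete graded comparison between arms of the mostly grade 2 effects behind the protocol's own safety concern

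*Combined protocol and SAP*

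**What the plan says.** Safety is a secondary objective (section 1.2: "To assess the safety of indoximod when administered post sipuleucel-T therapy") and a secondary endpoint (section 11.2: "Safety and tolerability") of a randomised, double-blind, placebo-controlled trial. Section 12 describes no between-arm safety analysis.

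The protocol names a specific risk. Section 2.3 says that when indoximod follows sipuleucel-T directly, "it might increase the side effects of cytokine release from last infusion of sipuleucel-T", and section 5.2.1 repeats this. Section 2.2 gives the usual severity: "Sipuleucel-T is very well tolerated with mostly grade 2 side effects consistent with cytokine release".

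Section 8.2 monitors adverse events from consent to the final treatment visit, about 30 days after the last dose. What must be documented is narrower: "adverse event documentation requirements will be determined based on grade, expectedness and relationship to study therapy". The table reads:

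| Attribution | G1 | G2 expected | G2 unexpected | G3 expected | G3 unexpected | G4-5 |
|---|---|---|---|---|---|---|
| Unrelated, unlikely | no | no | no | no | yes | yes |
| Possible, probable, definite | no | no | yes | yes | yes | yes |

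Under section 8.1 an event "is considered “unexpected” if it is not listed in the investigator brochure or is not listed at the specificity or severity that has been observed". Sections 8.3 and 8.4 separately require all serious events to be reported, whatever the attribution or expectedness.

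**The concern.** The grade that the protocol associates with cytokine release is the grade for which documentation is most often waived. In a double-blind trial the placebo arm allows a drug effect to be read from event counts without anyone judging cause patient by patient. A rule that admits events only after such a judgement gives up part of that advantage. A site that leans towards attributing fever to sipuleucel-T and a site that leans towards study drug would record different events from the same clinical picture.

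At stake is a reliable graded description, by arm, of fever and chills after the third infusion and of symptomatic effects such as fatigue, nausea, diarrhea and rash. Patient protection is not at stake, since serious events and stopping-rule events are captured in any case.

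**Working it through.** The plan states no figure on this point, so the main check sets the passages side by side. The arithmetic at the end only indicates size.

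**1. Cells waived at grade 2 and above.** Expected grade 2 is waived in both rows. Unexpected grade 2 is waived when unrelated or unlikely. Expected grade 3 is waived when unrelated or unlikely. That is 4 of the 8 cells at grades 2 and 3, and none at grades 4-5.

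**2. A grade 2 fever just after the third infusion.** Section 5.1.2 names pyrexia and rigors as common with sipuleucel-T. The indoximod list in section 5.2.1 has fever only with low white cells, and no chills or rigors.

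- Judged unrelated or unlikely: not required, whether expected or not.
- Judged at least possibly related and expected: not required.
- Judged at least possibly related and unexpected: required.

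The same event is documented on one of these three routes. Section 8.2 does not say whether the study therapy used for attribution includes sipuleucel-T, so sites may take different routes.

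**3. Indoximod's listed effects.** Section 5.2.1 lists 5 event types at 20% or more and 9 at 10 to 19%, so 5 + 9 = 14. Three are blood counts and 11 are symptoms. If listing makes an event expected, its grade 2 occurrences are waived under either attribution.

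**4. Other sources in both arms (sections 5.2 and 6.2, appendices IV and V).**

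- Blood counts and chemistry at every on-drug visit from week 6. These are numeric and can be graded afterwards.
- Autoimmune checklist at weeks 6, 8, 10, 14, 20 and 28. It is present/absent by organ system. Fatigue and fevers share one item; nausea, vomiting, diarrhea and abdominal pain share another. Chills and rigors do not appear.
- FACT-P, first given on study drug at week 8, with a 7-day recall.
- Patient log of side effects, daily through week 14. It is ungraded, and the documents do not say that its entries enter the database.
- Review of side effects at on-drug visits from week 6, with documentation still governed by the 8.2 table.

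Study drug starts the day after the third infusion, in week 4. None of these sources assures CTCAE-graded symptomatic events in the days that follow.

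**5. Stopping rule.** Section 12.2 counts related grade 3 events that do not resolve within 7 days and any grade 4-5 event. All fall in required cells.

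**6. Size, with assumed rates.** Arm size is 25 (section 12.1). For an assumed 30% v 10%, the expected counts are 25 × 0.30 = 7.5 and 25 × 0.10 = 2.5. The 95% half-width for the difference is 1.96 × √(0.30 × 0.70/25 + 0.10 × 0.90/25) = 1.96 × √0.0120 = 0.215.

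Exact power was found by summing the two binomial distributions over all outcomes with two-sided Fisher p ≤ 0.05:

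| Assumed rates | Fisher power | 95% half-width |
|---|---|---|
| 10% v 30% | 30% | 21 points |
| 20% v 40% | 23% | 25 points |
| 20% v 50% | 51% | 25 points |
| 20% v 60% | 79% | 25 points |

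An observed 8 v 2 gives p = 0.07, and 7 v 3 gives p = 0.29.

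**The case against.** The strongest reply is that all 14 event types listed at 10% or more are touched by some instrument applied alike in both arms. Nine symptoms are on the checklist, three items are blood counts, and appetite and bowel trouble are FACT-P items, with quality of life compared by arm in section 12. This stands. A reader might infer from the table that these events go unrecorded, or that the arms cannot be compared on safety. The documents do not support either inference. The table says that documentation is not required, which does not forbid it. Comparisons also remain possible on grade 4-5 events, related or unexpected grade 3 events, serious events and laboratory values.

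A reader might also infer that the rule leaves out exactly the cytokine-release events. That is not established: a grade 2 fever judged possibly related could count as unexpected and so be required. Nor is it right that grade 3 events are captured only if attributed to study drug. Unexpected grade 3 events are required whatever the attribution, expectedness depends partly on severity, and section 5.2.1 gives no grades.

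It can also be said that tiered collection is a reasonable choice in a 50-patient phase II trial, and that full capture would give only a low-powered table. The power figures bear this out. But where description is all the trial can offer, completeness matters more. The substitute sources are ungraded, grouped by organ system, or start at week 6 or later, so they do not close the gap for symptoms soon after the third infusion.

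**Conclusion.** The concern holds in a limited form. Section 8.2 does not assure a complete CTCAE-graded comparison between arms of the cytokine-release effects that the protocol worries about, or of indoximod's listed symptomatic effects. Capture depends on blinded attribution and expectedness calls. The size cannot be computed from the documents; under an assumed 30% v 10% it concerns about 10 affected men in total (7.5 + 2.5), some of whom sites might record anyway.

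The conclusion assumes that events listed in section 5.2.1 are ordinarily treated as expected at grade 2, and that sites document little beyond what is required. If sites recorded more, the gap would be smaller, though probably uneven between sites. Safety monitoring, the stopping rule and the primary analysis are unaffected. This is a cheap improvement to a secondary endpoint.

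**What to change.** In section 8.2, require documentation of every grade 2 or higher event, regardless of expectedness and attribution, from the third sipuleucel-T infusion through the final treatment visit. Starting at the infusion, not at the first study-drug dose the next day, makes events before study drug available as a reference. Keep attribution and expectedness as descriptive fields, and leave expedited reporting unchanged.

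In section 12, add a descriptive by-arm table of events by type and grade, with confidence intervals for the differences.

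The cost is more form entries for about 50 patients. The period lies within the monitoring window that section 8.2 already sets, and side effects are already reviewed at on-drug visits and logged by patients. The gain is limited to description: at 25 per arm, intervals for the differences would run to roughly plus or minus 20 to 27 points over a range of assumed rates, so the table should not be presented as a test.
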